- We assume a total of 31 participating colleges and an average of 60 students per college for each of the three pairwise comparisons, with 30 in each treatment arm and 30 in the control (with a broadly even split between maths and English). This means a total of 930 students in each treatment arm and 930 in the control group; a total of 1860 for each of the three pairwise comparisons.
- Maths and English outcomes (i.e. a pass or fail in the English or maths GCSE resit exam) will be considered together as a single outcome variable.
- We assume equal proportions of students in the treatment and control groups ($P = 0.5$) for each pairwise comparison.
- We anticipate a baseline pass rate of 30% ($\theta = 0.3$)
- We have three separate significance tests for the primary outcome, with each of the three treatment groups separately compared to the control group.
- We assume a nominal Type 1 error rate of 0.05 with a two-tailed test, amended using a Bonferroni adjustment for three separate independent tests, to a value of 0.0167 for each test. The Type II error rate is set at 0.2, giving power of 0.8.
- We assume¹⁴ an intra-cluster correlation coefficient (ρ) of 0.1.
- No between site heterogeneity is expected (i.e. $\omega = 0$).
- No level 1 baseline test covariate has been included in the calculation, for reasons explained below. There are also no level 2 stratification variables because we have treated the colleges as random effects and no preliminary stratification was undertaken for college type.
- We assume no attrition in the design, our rationale for which is explained below.
- The EverFSM MDE calculation combined all three treatment arms and assumed a 20% prevalence per college, giving $(90 \times 0.2) + (30 \times 0.2) = 24$ students per college.

The assumptions for each MDE estimation are given in Table 2, below.

The sample size calculations in Table 2 were originally intended to enable the detection of a seven percentage point increase in the GCSE pass rate, from (an estimated) 30 per cent to 37 per cent.¹⁵ However, the underlying model for the purposes of this power calculation, which we have now changed as described above, assumed, a fixed effects model, with no random variation at Level 2, i.e. colleges represented strata from a population fully defined by the sample.

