Analysis of the free school meal (FSM) students will combine all three treatment groups into a single group and compare them to the control group (i.e. a ratio of 3:1). We assume that 20 per cent of the overall group will be EverFSM, i.e. 48 out of 240 in each college.

We understand that the primary concern of the study is whether or not students pass their GCSE resit. Consequently, a binomial pass/fail measure is more appropriate than a continuous outcome for the current study. In addition, it is anticipated that re-sit scores will cluster around the pass/fail threshold, leaving a restricted range of scores on the Level 1-9 scale, which will not be suitable for analysis assuming a continuous measurement scale.²² (Unfortunately, it is not possible to obtain the raw GCSE marks (i.e. a percentages) underlying these grades from the NPD.)

In view of this, we propose that English and maths attainment scores for the end of the academic year of study be taken from the NPD and coded in binary format: a KS4 re-sit pass is defined as attaining level four or above; a fail is defined as reaching levels one to three. We will also classify young people who do not re-sit the exam as a 'fail', in line with the intention-to-treat approach. Outcome data will be obtained by matching pupils at the start of the academic year in the study to their outcome data for the end of the academic year. The outcome estimate will be a pass-rate proportion (a ratio of the number who started the trial and passed the exam divided by number starting the trial) bounded by zero and unity.

Each outcome has four intervention groups: three treatment and one control, and the aim is to test each treatment separately against the control group to determine the efficacy of each treatment. Consequently, we run three paired treatment–control tests. In order to maintain a five per cent significance level for each test, a standard Bonferroni adjustment was applied to account for the three tests in each of the families. This resulted in a value of 0.0167, i.e. $\alpha/3$, and only tests showing a significance level below this threshold will be accepted as statistically significant at $\alpha = 0.05$.

²¹ Analysis suggests that around 250 students entered their own number rather than their study supporter's, but that these cases were evenly distributed across colleges and treatment group. This issue will be discussed in more detail in the final evaluation report.

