Consequently, to adjust for any missingness in the outcome variables we want first to establish whether variables used to predict missingness are associated with the outcome variable. Once we have identified relevant variables with missingness the second step is to assess whether the pattern of missingness differs between treatment and control groups.

For the first step we will identify the association between our suite of variables in the NPD extract and our outcomes. Secondly, variables that are correlated with outcomes will be entered as predictors²³ into a logistic regression model where the dependent variable is the missing/non-missing indicator on the outcome variable. This will inform us of which predictor variables are related to missingness in the outcomes. The next step will be to enter the treatment indicator and a series of interaction terms between the treatment indicator and those variables with a significant main effect association with missingness. Finally, assuming significant associations are found for some of the interaction terms, we will run a reduced form of the model including only significant interaction terms and their associated main effects from the previous model. From this we will construct a missingness weight as the inverse of the propensity score from the reduced model. We will then rerun models (1) and (2) above to explore the adjustment on the magnitude of the impact estimator. Stata's complex survey suite of models will be used (svyset) in order to adjust appropriately for the weight on the variance estimator of the impact effect.

Non-compliance with intervention

There is no a-priori clear cut measure of the number of texts a student should receive for the treatment to be effective; consequently, we do not have a theoretical basis to assign compliance as a function of the number of texts sent and/or received. However, we can consider the proportion defined as a function of the number of texts received divided by the maximum number of texts issued to an individual. In the first instance we will consider compliance as receiving all texts and non-compliance as anything less than all. Depending upon the distribution of texts received, we will consider lowering the threshold for compliance to less than 100 per cent to a lower threshold and using values above that threshold as compliance and below as non-compliance.²⁴ This will act as a sensitivity test for our compliance estimate.

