²³ We intend to deal with missingness in predictor variables through dummy coding missing as an explicit categorical indicator for each variable included in the model.

²⁴ The BIT texting platform allows the developer to monitor the number of 'bounce-backs' (i.e. messages which could not be delivered). This number is available for each weekly 'batch' of text messages sent.

A common approach to estimating compliance has arisen from Bloom (1984)²⁵ and Imbens and Angrist (1994)²⁶ which use an instrumental variables approach to identify compliance. Allocation to treatment group under randomisation acts as an instrument allowing estimation of treatment on those who have complied with treatment. This approach identifies four possible groups of people in terms of their potential assignment and response to treatment offer:

- Defiers: people who do the opposite to whatever action they are assigned
- Never takers: people who always refuse treatment on offer
- Always takers: people who find treatment whatever their allocation
- Compliers: people who take the treatment if offered, but otherwise do not

We assume that never-takers and always-takers do not contribute to the treatment effect (e.g. Bloom, 2006; p10), leaving a treatment effect created by compliers and defiers. Thus:

$$LATE = \frac{ITT}{E(D|Z = 1) - E(D|Z = 0)} \quad (3)$$

Where LATE is the local average treatment effect and represents the treatment effect as the impact on compliers. Z refers to the instrument, i.e. the group to which a person is allocated through random assignment and D represents treatment received (0 = no, 1 = yes).

In the present design we consider it extremely unlikely that people outside of the treatment group seek out supportive texts in a way that mirrors treatment.²⁷ Consequently, we assume that $E(D|Z = 0) = 0$. Formula 3 then reduces to:

$$TOT = \frac{ITT}{E(D|Z = 1)} \quad (4)$$

Where TOT is treatment on the treated. Typically, the TOT represents a weighted average of always takers and compliers.

We note that we can represent the ITT as an odds ratio or on proportional scale, i.e. the difference between two proportions, and will present both versions in the report, in compliance with EEF guidelines for binomial outcome data. We will calculate ITT and TOT on both scales for all impact analysis undertaken.

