We also note that potentially we can extend the compliance estimator using the distribution of the proportion of compliance to create separate 'groups' for each level of compliance (e.g. group 1 = compliance < 25%, 2 = 50% etc.). If we have sufficient numbers in each group, we could calculate an 'average causal response with treatment intensity' (ACLTI) (Angrist and Pischke, 2009, Section 4.5.3).²⁸ This approach uses two-stage least squares to weight together the estimates across the compliance groups. We will update the analysis plan accordingly should the distribution of non-compliance²⁹ allow for a reasonable estimation of ACLTI.

Secondary outcome analyses

We originally proposed in the protocol to analyse attendance in class as a continuous outcome defined as the proportion of classes attended out of the total number taught. On reflection, it seems

²⁵ Accounting for No-Shows in Experimental Evaluation Designs
<https://doi.org/10.1177/0193841X8400800205>

²⁶ Identification and Estimation of Local Average Treatment Effects
<http://www.nber.org/papers/t0118>

²⁷ In principle, it is possible that people send themselves weekly text reminders which are similar to those used in the experiment but we will not know that from our design.

²⁸ Angrist, J. D., & Pischke, J. (2009). *Mostly harmless econometrics: An empiricist's companion*. Princeton: Princeton University Press.

²⁹ We will not know the full extent of non-compliance, i.e. drop out/bounce-back until the end of the experiment because people can drop out at any time.

more appropriate to consider this as a binomial outcome because the binomial distribution will bound predicted proportions between unity and zero. In other words, attendance at each session will be treated as a binary outcome (attended/not attended). We will use a logit model to explore the proportion of sessions attended versus the total number of sessions. In addition, we will amend the proposed CACE analysis to be appropriate to a binary outcome (see below). Therefore, analysis of the secondary outcomes takes the same form as model 2, where $\pi_i = \frac{Y_i}{X_i}$, where X is the total number of classes and Y is the total number of classes attended, i.e.

$$\text{logit}(\pi)_{ij} = \beta_{0j} + \beta_{1j}\text{treatment}_{ij} + r_j \text{ (Treatment = Student text only)}$$

$$\text{logit}(\pi)_{ij} = \beta_{0j} + \beta_{1j}\text{treatment}_{ij} + r_j \text{ (Treatment = Supporter text only)}$$

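### The compliance formula is valid for a difference in proportions but not for an odds ratio, yet the SAP commits to the treatment-on-the-treated effect on both scales and gives no other odds-scale estimator

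*SAP*

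**What the plan says.** The SAP section on non-compliance with the intervention starts from the instrumental-variables ratio in formula (3), which divides the ITT effect by the difference in receipt between the arms. Control-arm receipt is then set to zero: "In the present design we consider it extremely unlikely that people outside of the treatment group seek out supportive texts". This gives formula (4), TOT = ITT / E(D|Z=1), the only TOT formula in the document.

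The text after formula (4) names two scales: "We note that we can represent the ITT as an odds ratio or on proportional scale", the latter being the difference between two proportions. It then commits: "We will calculate ITT and TOT on both scales for all impact analysis undertaken". It gives no log-odds step and no separate estimator for the odds ratio.

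Compliance is strict at first: "In the first instance we will consider compliance as receiving all texts and non-compliance as anything less than all". The Introduction puts the number of texts at 36 or 37. The rate is not known in advance (footnote 29): "We will not know the full extent of non-compliance, i.e. drop out/bounce-back until the end of the experiment". One source is quantified, in footnote 21: "around 250 students entered their own number rather than their study supporter's".

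The section on secondary outcome analyses says that the complier analysis will be adapted to a binary outcome and points to later text. No such adaptation follows. Formula (5), under effect size calculation, only turns logistic coefficients into a relative risk.

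**The concern.** Formula (4) rests on the assumption that people whose receipt does not depend on allocation add nothing to the effect. On a difference scale, adding nothing means adding 0. The ITT difference is then c times the complier difference, and dividing by c recovers it. An odds ratio has no such property: its null value is 1, and dividing it by c < 1 moves that null to 1/c.

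The commitment covers all impact analyses, so it reaches the three arm comparisons and attendance. One report could show a TOT of zero percentage points beside a TOT odds ratio well above 1, from the same data. Because the SAP offers no alternative, the analyst must either apply an invalid formula or choose another one after seeing the data.

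**Working it through.** **Inputs from the SAP**
- Control pass rate: "We anticipate a baseline pass rate of 30" per cent (Calculation of sample size).
- Minimum detectable effect (MDE): 6.8 percentage points (Table 2). The design target was a rise "from (an estimated) 30 per cent to 37 per cent".
- Own-number cases: about 250 (footnote 21), of 3,823 randomised (Table 1).
- Control-arm receipt: 0.

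**Inputs that are assumptions**
- Compliance c of 0.9, 0.8 and 0.7. The SAP gives no rate.
- A control pass rate among compliers of 30%, the same as overall.
- A harmful ITT result of 30% to 27%, for illustration.

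**1. The plan's own figure.** The SAP states no TOT value, so the figure to reproduce is the MDE. Formula (1) with ω = 0, ρ = 0.1, no covariates, J = 31, n = 60 and P = 0.5 gives √(0.9 / (0.25 × 31 × 60)) = 0.0440. Multiplying by √(0.3 × 0.7) = 0.4583 gives 0.02016. With 30 degrees of freedom and two-sided α of 0.0167, the multiplier is about 3.389, so the MDE is 6.83 points. The stated 6.8 is reproduced.

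**2. Compliance implied by the one quantified source.** 250 / 3,823 = 0.065, so c is about 0.935 if these students are the only non-compliers and are spread evenly, as footnote 21 says.

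**3. ITT odds ratios**
- MDE: (0.368/0.632) / (0.30/0.70) = 1.359.
- Harmful: (0.27/0.73) / (0.30/0.70) = 0.863.

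**4. Formula (4) applied to the odds ratio (OR/c), against the complier odds ratio.** The latter uses the valid step: complier treated rate = 0.30 + (ITT difference)/c, converted to an odds ratio against 0.30.

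| c | Null: OR/c | Null: complier OR | 27% v 30%: OR/c | 27% v 30%: complier OR | 36.8% v 30%: OR/c | 36.8% v 30%: complier OR |
|---|---|---|---|---|---|---|
| 0.935 | 1.07 | 1.00 | 0.92 | 0.85 | 1.45 | 1.39 |
| 0.9 | 1.11 | 1.00 | 0.96 | 0.85 | 1.51 | 1.40 |
| 0.8 | 1.25 | 1.00 | 1.08 | 0.83 | 1.70 | 1.46 |
| 0.7 | 1.43 | 1.00 | 1.23 | 0.81 | 1.94 | 1.54 |

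Example, last row, MDE: 1.359/0.7 = 1.94. The valid route gives 0.068/0.7 = 0.0971, a complier treated rate of 0.397, and (0.397/0.603) / (0.30/0.70) = 1.54.

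**5. When the sign reverses.** OR/c exceeds 1 while OR is below 1 exactly when c < OR < 1. For 0.863 this happens at c = 0.8 and 0.7, but not at 0.9 or 0.935.

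**6. The log-odds alternative.** exp(ln OR / c) keeps 1.00 at 1.00 and keeps the sign. At the MDE with c = 0.7 it gives exp(ln 1.359 / 0.7) = 1.55, against 1.54. It is only approximate, because it depends on the compliers' own baseline. For an ITT change of 30% to 35% with c = 0.5 it gives 1.58. The complier odds ratio is 1.71 if the compliers' control rate is 20% (30% v 20%) and 1.50 if it is 50% (60% v 50%).

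**The case against.** The strongest defence is that the SAP never writes an odds ratio divided by the compliance rate. Formula (4) is stated for a generic ITT. The fitted models are logistic, so their treatment coefficient is a log odds ratio. An analyst might divide that coefficient and exponentiate, or compute the TOT as a difference and re-express it. Both keep the null at 1 and preserve the sign, and step 6 shows that the log-odds version can come close. This stands as a caution: a reader might infer that the invalid division is certain to be carried out, and the text does not go that far. It does not remove the fault. Neither route is in the SAP, and the literal reading of the formula together with the commitment to both scales is invalid.

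A reader might also infer that every odds-ratio TOT would lean towards benefit whenever compliance is incomplete. That is not a general result. For 30% to 60% with c = 0.5, OR/c is 3.5/0.5 = 7. The complier rates are 90% against 30%, an odds ratio of 9/(0.30/0.70) = 21, so here the division understates the effect. So large an effect is far beyond what the trial was designed for.

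The size of the error rests on compliance, which the SAP does not give. The own-number cases alone move the null only to 1.07. The requirement to receive every text could push c lower, but by an unknown amount.

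Lastly, the TOT is supplementary, and the valid proportion-scale result would stand beside it and show up any conflict. That argues for lower severity, not for leaving the text as it is.

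**Conclusion.** The point holds in a limited form. As written, the SAP applies to an odds ratio a formula that is valid only for a difference in proportions, and it supplies nothing else for that scale.

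The shift of the null to 1/c is exact arithmetic. Its size is conditional: 1.07 from the only source of non-compliance that the SAP quantifies, and 1.11 to 1.43 for assumed compliance of 0.9 to 0.7. The comparison at the MDE (1.94 against 1.54 at c = 0.7) also assumes a 30% control pass rate among compliers. Reversal of a harmful result is possible but needs c < OR < 1.

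A reader might take this as a threat to the trial's main conclusion. It is not: the primary ITT tests, the Bonferroni threshold, the sample size, the relative-risk effect size and the proportion-scale TOT do not use the faulty step. The point should be fixed, but it is not critical to the primary result.

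**What to change.** - State that formula (4) is applied only to the difference in proportions, for both pass rate and attendance, and is not applied to the odds ratio. Amend the commitment to both scales to match.
- If a ratio for compliers is wanted, derive it from estimated complier rates. Take the observed rate in treated compliers, p1c, and set the complier control rate to p1c − TOT. The relative risk is p1c / (p1c − TOT), and the odds ratio comes from the same two rates. In the example at c = 0.7, 0.397 against 0.300 gives a relative risk of 1.32 and an odds ratio of 1.54.
- Give a bootstrap or delta-method interval. Do not report the ratio if the implied control rate falls outside 0 to 1, or on a boundary where the ratio is undefined.
- Let this text also supply the binary-outcome complier analysis that the attendance section promises.

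Two-stage least squares with college terms is optional, since the simple ratio is already valid on the proportion scale. The cost is SAP wording and a little extra analysis; no new data are needed.

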The MDES is the standardised minimum detectable effect size, i.e. the minimum impact we would expect the experiment to detect with the given sample size and design. Where M_{J-g^*-1} is the sum of the t values corresponding to the appropriate levels of the Types I and II error levels, with the appropriate degrees of freedom, R^2 is the proportion of variance explained by covariates entered at the appropriate level of the hierarchical model; ρ is the intra-cluster correlation, ω is the between site treatment heterogeneity effect, J is the number of clusters (colleges) and n is the average number of students per college.

Given (from Bloom, 2006;¹³ equation 4) that

$$ES = \frac{\bar{Y}_t - \bar{Y}_c}{\sigma}$$

We can simply multiply the MDES, calculated through PowerUp, by σ to get the MDE, i.e. the minimum impact effect stated as a difference using the scale of a proportion. We know σ from the binomial nature of the data, i.e. $\sigma^2 = \theta \times (1-\theta)$, where we will take θ to be the proportion anticipated achieving success in the control group.

Our assumptions in calculating the MDE are as follows:

- We have a 2-level multi-level model with allocation to treatment modelled as a fixed effect at level 1 (students), with colleges (level 2) allowed to vary randomly with respect to student outcomes (i.e. $r_{ij} \sim N(0, \sigma^2)$).

⁸ Statistical Analysis Guidance, 2018, p. 5.

⁹ Demidenko, E. (2007) Sample Size Determination for Logistic Regression Revisited. *Statistics in Medicine*, 26, pp. 3385-3397, available at: <http://dx.doi.org/10.1002/sim.2771>

¹⁰ Going beyond simple sample size calculations: a practitioner's guide
<https://www.ifs.org.uk/publications/7844>

¹¹ Estimators for Clustered Education RCTs Using the Neyman Model for Causal Inference
<http://journals.sagepub.com/doi/pdf/10.3102/1076998611432176>

¹² Dong, N. and Maynard, R. A. (2013) PowerUp!: A tool for calculating minimum detectable effect sizes and sample size requirements for experimental and quasi-experimental designs. *Journal of Research on Educational Effectiveness*, 6(1), pp. 24-67, doi: 10.1080/19345747.2012.673143

¹³ The Core Analytics of Randomized Experiments for Social Research. MDRC Working Papers on Research Methodology, available at: <https://files.eric.ed.gov/fulltext/ED493363.pdf>

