²² The NPD does contain semi-continuous scores (from 1-9) for GCSE maths and English resit students. However, students retaking exams as part of the new requirement are likely to be at a very similar academic level, thus likely to obtain results which cluster around the same two or three grades (3-5). We therefore feel there is very limited value in using these grades.

Secondary outcomes

Students' records of attendance will be collected from colleges directly using a secure data transfer; (datasets being shared via secure Natcen's File Transfer Protocol (FTP) site). This will be a simple attendance record stating whether students were present or absent for each class. This will allow for the creation of a variable recording the overall attendance rate, i.e. the proportion of classes attended to all classes given for the course (i.e. attendance at each class taken as a binary variable), for each pupil in the study.

Data on student aspirations, confidence and attitudes to learning will be recorded as part of the process evaluation and does not constitute part of the impact evaluation.

Analysis

Primary intention-to-treat (ITT) analysis

It is proposed to run an intention-to-treat analysis, with a binomial outcome defined as passes in the numerator and failures and no shows in the denominator, as described above. This will involve running separate models for each of the three paired outcomes, i.e. each treatment group compared separately to the control group, where the significance level of the test will be conducted using the adjusted Bonferroni level. We propose to use a binomial multilevel logistic regression model, with students at Level 1 nested within colleges at Level 2, and colleges will be allowed to vary randomly, with a residual mean centred at zero with a Gaussian distribution.

The basic form of the model is:

$$\text{logit}(\pi)_{ij} = \beta_{0j} + \beta_{1j}\text{treatment}_{ij} + r_j \quad (2)$$

We will run separate models for each treatment comparison group as follows:

$$\text{logit}(\pi)_{ij} = \beta_{0j} + \beta_{1j}\text{treatment}_{ij} + r_j \quad (\text{Treatment} = \text{Student text only})$$

$$\text{logit}(\pi)_{ij} = \beta_{0j} + \beta_{1j}\text{treatment}_{ij} + r_j \quad (\text{Treatment} = \text{Supporter text only})$$

$$\text{logit}(\pi)_{ij} = \beta_{0j} + \beta_{1j}\text{treatment}_{ij} + r_j \quad (\text{Treatment} = \text{Student and Supporter text jointly})$$

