The EEF guidance suggests the use of a relative risk ratio (RR) as an effect size for binary outcomes. Consequently, this is what we propose to use here for each of the three models making up our primary outcomes. We note that the primary outcome models proposed here are relatively simple and do not include controls for covariates. This is advantageous given that the RR can vary conditional upon covariate levels and would require the centring of covariates in the logistic model to assess the RR at its average covariate value. However, we do not have this issue with the models proposed here, but the Level 2 random college effect will translate into the odds for students at the average level of success across colleges.

The protocol did not specify the calculation of effect sizes for the primary outcomes but did propose an effect size appropriate to continuous outcomes for class attendance. As noted above, we now propose to treat the model for class attendance using a binomial distribution appropriate to modelling differences in proportions. We therefore propose to use the relative risk ratio as a measure of the effect size for this outcome

We will calculate the relative risk ratio, following a method outlined by Fleiss & Berlin (2009),³⁰ as the measure of effect size, using the results, as appropriate, from the three versions of model (2) above for each of the treatment groups and for the class attendance model.

$$RR = \frac{1 + \exp^{-\alpha}}{1 + \exp^{-\alpha - \beta}} \quad (5)$$

In (5) above α refers to the constant from the logistic model (2) and β refers to the treatment indicator.

³⁰ Cooper, H., Hedges, L. and Valentine, J. *The handbook of research synthesis and meta-analysis*

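### The attendance model has no term for repeated sessions within a student, so any positive within-student correlation makes its standard errors too small

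*SAP*

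**What the plan says.** The SAP, under "Secondary outcome analyses", drops the protocol's continuous per-student proportion. In its place "attendance at each session will be treated as a binary outcome (attended/not attended", and "analysis of the secondary outcomes takes the same form as model 2", "where X is the total number of classes and Y is the total number of classes attended". The section "Effect size calculation" confirms the distribution: "we now propose to treat the model for class attendance using a binomial distribution appropriate to modelling differences in proportions".

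Model (2) is defined under Primary intention-to-treat (ITT) analysis, with "students at Level 1 nested within colleges at Level 2, and colleges will be allowed to vary randomly". The three attendance equations repeat that form: an intercept, a treatment coefficient and the college residual r_j. No student-level random effect, overdispersion term or student-clustered variance is named. The only variance estimator that is not purely model-based is Stata's survey suite under "Missing data", and it is brought in for the missingness weight, "in order to adjust appropriately for the weight on the variance estimator of the impact effect".

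The reason given for the change is that a binomial model keeps predicted proportions between zero and one.

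**The concern.** Model (2) suits the pass/fail outcome because each student supplies one result. For attendance each student supplies X results. A binomial likelihood for Y out of X is the likelihood of X independent sessions given college and arm.

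Treatment was allocated to students within colleges, so the college intercept cannot absorb differences between students in the same college. Those differences are the noise against which the arms should be compared. The SAP also expects some students to leave college ("Attrition and Follow-up"). If classes after they leave count in the denominator, this would produce long runs of absences in single students.

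Keeping predictions within bounds justifies the logit link. It does not justify the binomial variance.

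Attendance is the only secondary outcome in the impact evaluation, and better attendance is one of the programme's stated aims. Chance differences between arms could be reported as effects, in either direction, with intervals that are too narrow.

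**Working it through.** **The SAP's own figure.** No sample size, power or standard error is given for attendance. The primary minimum detectable effect can be reproduced from formula (1) with ω = 0, no covariates, ρ = 0.1, P = 0.5, J = 31, n = 60, θ = 0.3 and 30 degrees of freedom (M = 3.3895):

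3.3895 × √(0.9 / (0.25 × 31 × 60)) × √0.21 = 0.0683, or 6.8 points, as in Table 2.

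The EverFSM figure also reproduces (10.66 against 10.7). Both concern an outcome with one observation per student, so the problem below does not touch them.

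**Inputs for attendance.**
- From the SAP: 31 colleges, 60 students per college in each pairwise comparison, equal allocation, and a Bonferroni level of 0.0167 (z = 2.394). The Bonferroni rule is set out for the primary outcome. Its use for attendance is an assumption.
- Not in the SAP, so assumed: sessions per student m = 30 to 120, and within-student correlation ICC = 0.05 to 0.3.

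**Formulas.** Design effect DE = 1 + (m − 1) × ICC. The standard error is understated by √DE. The true two-sided type I error is 2 × (1 − Φ(z / √DE)).

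| m | ICC | DE | √DE | Type I at 0.0167 | Type I at 0.05 |
|---|---|---|---|---|---|
| 30 | 0.05 | 2.45 | 1.57 | 13% | 21% |
| 36 | 0.1 | 4.5 | 2.12 | 26% | 36% |
| 60 | 0.2 | 12.8 | 3.58 | 50% | 58% |
| 100 | 0.3 | 30.7 | 5.54 | 67% | 72% |
| 120 | 0.3 | 36.7 | 6.06 | 69% | 75% |

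For example, the last row has DE = 1 + 119 × 0.3 = 36.7, √36.7 = 6.06, and 2 × (1 − Φ(2.394 / 6.06)) = 0.69.

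**Simulation under the null.** The settings were 31 colleges of 60 students, mean attendance about 75% (assumed), beta-binomial students, m of 36, 60 or 100, ICC of 0.05 to 0.3, and 400 runs per setting. A binomial logit was fitted with college dummies. The SAP specifies a random college intercept, but with the arms balanced within each college the two should differ little.
- Model-based standard errors: false positives at 0.0167 ran from 17% (m = 36, ICC 0.05) to 72% (m = 100, ICC 0.3). At 0.05 they ran from 24.5% to 77.5%.
- Ratio of robust to model-based standard error: 1.64 to 5.51, in line with √DE.
- Student-level robust standard errors: 3.3% to 7.5% at nominal 5%, averaging 5.3% over the twelve settings. One setting has a simulation error of about √(0.05 × 0.95 / 400) = 1.1 points.

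**Could another term in the model absorb the excess?** The treatment coefficient carries a college subscript, and a random treatment slope by college would pick up part of it. None is specified, however. The power section has "allocation to treatment modelled as a fixed effect at level 1 (students" and sets between-site heterogeneity to zero.

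**The case against.** The best defence is that one row per student was intended. "Secondary outcomes" defines an attendance rate for each pupil, and the model section indexes Y and X by student and speaks of the proportion attended. A fractional logit with robust errors would fit that wording. Against this, the SAP makes each session a binary outcome and names the binomial distribution. Grouping sessions into one row per student leaves the binomial likelihood for the coefficients unchanged, so it cures nothing. If a fractional logit was meant, the SAP must say so and name the variance estimator.

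It could also be said that Level 1 already represents students. It does, but a binomial logit has no free Level 1 variance, so naming that level adds no allowance for differences between students.

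The objection that the size is unknown stands. The document gives no session count, attendance rate or within-student correlation, and only the direction follows from it. It is also fair that the secondary section states no significance level, so 0.0167 is inferred. That does not help the plan, because the inflated error rate is higher still at 0.05.

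Finally, attendance is secondary. This limits the damage but does not make the inference valid.

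**Conclusion.** Wrong as written. The direction needs only more than one session per student and a positive correlation between a student's sessions: standard errors are then too small and type I error is above nominal. The size rests on assumptions. With 30 to 120 sessions and a correlation of 0.05 to 0.3, standard errors are about 1.6 to 6 times too small, and type I error is about 13% to 69% at 0.0167 if that level is used.

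Three stronger readings are tempting and are not supported:
- A reader might infer that the standard errors are known to be several times too small. The SAP has no figures to establish that, and the low end of the assumed range is well under two.
- A reader might infer that the trial's main result is at risk. The pass/fail outcome has one observation per student, and its 6.8-point minimum detectable effect stands.
- A reader might infer that the estimated attendance effect is biased. The fault shown here lies in the standard errors and tests; nothing shows material bias in the estimate.

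**What to change.** Analyse one attendance proportion per student by fractional logit, with college terms and student-level robust standard errors. This matches the per-pupil rate defined under "Secondary outcomes" and gives each student equal weight. It still keeps predictions between zero and one, which was the stated reason for the change.

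Name this one model as primary for attendance, because the alternatives estimate different things. A binomial model with robust errors weights students by their number of sessions, and a student random intercept gives an effect conditional on the student. A model with a student-level random intercept beneath the college intercept, with effects averaged over students, can serve as a sensitivity analysis.

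Take the risk difference and relative risk from averaged predictions instead of formula (5). Use the same variance for the attendance treatment-on-the-treated estimate and for any rerun with missingness weights. State the significance level that applies to the three attendance comparisons.

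The cost is a revised paragraph in the SAP, a small amount of extra Stata code and wider confidence intervals. No new data are needed.
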